9.2. Sample Size Determination

Sample size determination is based on the co-primary endpoint of height growth, defined as change from baseline of height at 12 months for participants on drug versus change from baseline of height at 12 months for a reference achondroplasia population. A total of 54 participants randomized to three dose levels in order to obtain 15 participants per dose, assuming a one-sided family-wise error rate of 0.05 with a Bonferroni correction (0.017 after Bonferroni adjustment for 3 comparisons), and inter-participant variability of .15 (estimated from C4181001), there is over 90% power to detect at least one dose providing 50% height growth above reference. No statistical comparison will be made between recifercept doses.

PK Study Cohort:

No formal sample size calculation was performed and 12 participants will be selected empirically to characterize PK, safety and tolerability after single 3 mg/kg dose administration of two formulations.

9.3. Analysis Sets

For purposes of analysis, the following analysis sets are defined:

Participant Analysis Set	Description
Full Analysis Set (FAS)/Safety	All participants receiving at least one dose of recifercept. Participants will be analyzed according to the dose they actually received.
Per-protocol analysis set (PPAS)	All participants receiving at least one dose of recifercept and have complete data at baseline through month 12 and without protocol deviations that were thought to impact the efficacy evaluation during the treatment period. Participants will be analyzed according to their randomized dose.
PK Concentration set	All participants who received at least one dose of recifercept and have at least one evaluable concentration result.
PK Study Cohort	All participants who received a dose of the recifercept Phase 2 formulation and a dose of the Phase 3 formulation with at least one evaluable concentration result.
PK Study Cohort Parameter (PKCP)	All participants in the PK cohort who have at least one PK parameter of interest.

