4. STUDY DESIGN

4.1. Overall Design

This is a phase 2 randomized, 3 arm (3 active doses of Recifercept), parallel group dose- finding study of safety, tolerability, PK and efficacy.

The study will enroll approximately 54 children with achondroplasia aged 2-10 years (inclusive) who will be enrolled and randomized to receive one of three doses of reciferecept (1 mg/kg once-weekly, 2 mg/kg twice-weekly or 1.5 mg/kg once-daily, n=18 per dose) such that approximately 45 participants are evaluable (up to 15 participants per dose). Additionally, **CCI** cohort of approximately 9 children with achondroplasia, ages 3 months to 2 years, will be enrolled later in the study (n=3 per dose). All 63 participants in this part of the study will receive reciferecept for 12 months.

PK Study Cohort:

At selected sites only, an additional PK cohort has been added to evaluate the PK of two reciferecept formulations. A total of 12 children with achondroplasia aged 2- < 11 years will be enrolled in the PK cohort (6 in each treatment sequence). Each participant will receive 2 treatments (3 mg/kg Phase 2 formulation [process 1c] and 3 mg/kg Phase 3 formulation [process 2]) in a randomized manner according to one of two sequences as outlined in [Table 1](#) below. Dose of the cohort could be changed due to emerging safety and efficacy data in the study.

PK samples collected following each dose will be analyzed to evaluate the exposures of two formulations.

Table 1. Treatment Sequence

Sequence	Period 1	Period 2
1 (n = 6)	Phase 2 study (process 1c) Formulation	Phase 3 study (process 2) Formulation
2 (n = 6)	Phase 3 study (process 2) Formulation	Phase 2 study (process 1c) Formulation

All participants who complete the study and in the opinion of the investigator, continue to have a positive risk: benefit profile, will be offered to enroll into an open-label extension (OLE) study. Participants will continue to receive recifercept at the dose previously received in this phase 2 study or at the therapeutic dose once this is identified.

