6.6.1. Rules for Progression to Next Enrollment Block

The eDMC will meet after block A participants have received 4 weeks of study intervention (completed D29) to review safety and PK data. They will make recommendations on dose levels and progression to block B.

Progression to blocks C and D, will occur without eDMC review if NONE of the following criteria are met:

- Serious Adverse Reaction (IMP-related SAR);
- ≥ 2 participants affected by the same moderate/severe study intervention-related AE;
- ≥ 2 participants affected by an AE of hypersensitivity to study intervention;
- ≥ 2 participants with severe ISRs;
- ≥ 2 participants with ISR leading to withdrawal of study intervention.

If any of these criteria are met then the eDMC must be convened to make a decision on progression to the next enrollment block. In addition, no further participants will be enrolled at that dose (or higher) until eDMC recommendation has been issued.

A sentinel approach will be used in recruiting those aged 2- <6 years in block C such that n=2 at high dose will be dosed followed by a 2-week delay before further dosing occurs in that age group.

The dosing schedule may also be adjusted by the eDMC to expand a dosing cohort to further evaluate safety and/or PK findings at a given dose level or to amend the doses to be studied in each enrollment block. The study procedures for these additional participant(s)/cohort(s) will be the same as that described for other study participants/cohorts.

In addition, following evaluation of the overall benefit:risk assessment at the interim analysis, the dose levels may be adjusted. If a new dose level is introduced then this will form a new cohort (minimum n=15) of treatment naïve participants. Previously treated subjects at a discontinued dose will be moved to the next lowest continuing dose.

Any dose modifications will not exceed the current maximum dose (1.5mg/kg once-daily) without submission and approval of a protocol amendment.

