9.4.2. Primary Endpoint(s)

Efficacy

The primary efficacy endpoint of change from baseline of height at 12 months will be analyzed using an analysis of variance (ANOVA) model comprising terms for reciferecept dose groups. Change from baseline estimates for height and their corresponding 95% confidence intervals will be provided via least-square means. A Bonferroni adjustment will be applied to the 95% confidence intervals. The population for the primary analysis will be based on the FAS, while the PPAS is the population that will be used for sensitivity analysis.

Safety

The safety data will be summarized in accordance with Pfizer Data Standards. All participants who receive IP (safety population) will be included in the safety analyses. All safety data will be summarized descriptively through appropriate data tabulations, descriptive statistics, categorical summaries, and graphical presentations. Safety endpoints for the study include:

- TEAEs and SAEs;
- Withdrawals from treatment due to AEs.

Change from baseline in laboratory data and vital signs will be additionally summarized. Participant listings will also be produced for these safety endpoints.

PK Study Cohort:

The pharmacokinetic parameters following single dose administration in the PK cohort will be derived from the concentration-time profile as follows:

Parameter	Definition	Method of Determination
AUC _{inf}	Area under the serum concentration time profile from time 0 extrapolated to infinite time.	AUC _{last} + (C _{last} * / k _{el}), Where C _{last} * is the predicted serum concentration at the last quantifiable time point estimated from the loglinear regression analysis.
AUC ₁₆₈	Area under the serum concentration-time profile from 0 to 168 hours.	Linear/Log trapezoidal method.
AUC ₃₆₀	Area under the serum concentration-time profile from 0 to 360 hours.	Linear/Log trapezoidal method.
C _{max}	Maximum serum concentration.	Observed directly from data.
T _{max}	Time for C _{max} .	Observed directly from data as time of first occurrence.
t _{1/2}	Terminal elimination half-life.	Log _e (2)/k _{el} , where k _{el} is the terminal phase rate constant calculated by a linear regression of the loglinear concentration time curve. Only those data points judged to describe the terminal loglinear decline will be used in the regression.

Actual PK sampling times will be used in the derivation of PK parameters.

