4. ANALYSIS SETS (POPULATIONS FOR ANALYSIS)

Data for all participants will be assessed to determine if participants meet the criteria for inclusion in each analysis population prior to unblinding and releasing the database and classifications will be documented per standard operating procedures.

Population	Description
Full Analysis Set (FAS)/Safety	All participants receiving at least one dose of reciferecept. Participants will be analyzed according to the dose they actually received.
Per-Protocol Analysis Set (PPAS)	All participants receiving at least one dose of reciferecept and have complete data at baseline through month 12 and without protocol deviations that were thought to impact the efficacy evaluation during the treatment period. Participants will be analyzed according to the randomized intervention.
PK Concentration set	All participants who received at least one dose of reciferecept and have at least one evaluable concentration.
PK Study Cohort	All participants who received a dose of the reciferecept Phase 2 formulation and a dose of the Phase 3 formulation with at least one evaluable concentration result.

Population	Description
PK Study Cohort Parameter (PKCP)	All participants in the PK cohort who have at least one PK parameter of interest.

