6. ANALYSES AND SUMMARIES

6.1. Primary Endpoint(s)

6.1.1. Increase in height growth above expected in reference population

6.1.1.1. Main Analysis

- Estimand strategy: Hypothetical ([Section 2.1.1](#)).
- Analysis set: FAS ([Section 4](#)).
- Analysis methodology: Change from baseline relative to Merker (2018) will be analyzed using MMRM including data from Months 3, 6, 9, and 12 with gender (and possibly age) as a covariate, subject (and/or time) as a random effect and an unstructured covariance matrix ([Section 5.2.1](#)).
- Intercurrent events and missing data: Data after study drug discontinuation and rescue will be excluded; intermediate missing values will not be imputed.
- The sample size, mean, standard deviation, median, minimum, and maximum at the baseline and postbaseline visits for observed standing height and change from baseline will be presented for each treatment arm.
- The least-squares (LS) means, the 95% confidence interval for the LS means, the difference between the LS means for each pair of treatment groups, and the corresponding 95% confidence interval will be presented for change from baseline in standing height for all postbaseline visits.

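### The efficacy set is grouped by dose received, but no rule says which arm a child belongs to after a protocol-permitted move to a lower dose

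*Protocol*

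**What the plan says.** The design statement in Protocol 4.1 reads: "This is a phase 2 randomized, 3 arm (3 active doses of Recifercept), parallel group dose- finding study".

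Protocol 9.3 defines a single set, labelled both full analysis set (FAS) and Safety, of everyone given at least one dose, and adds: "Participants will be analyzed according to the dose they actually received". SAP 4 uses the same rule. The per-protocol set (PPAS) goes the other way. The protocol says "Participants will be analyzed according to their randomized dose" and the SAP says "Participants will be analyzed according to the randomized intervention". That set is limited to children with complete data to Month 12 and no deviation thought to affect efficacy.

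The FAS carries the primary efficacy analysis in both documents. Protocol 9.4.2 has "The population for the primary analysis will be based on the FAS", and SAP 6.1.1.1 has "Analysis set: FAS". SAP 7.2 uses it for the interim too. The PPAS serves as a sensitivity analysis.

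Protocol 6.6.1 provides for dose changes during the trial: "following evaluation of the overall benefit:risk assessment at the interim analysis, the dose levels may be adjusted". It continues: "Previously treated subjects at a discontinued dose will be moved to the next lowest continuing dose". By Protocol 9.5 the interim falls when about 45 children have completed 6 of the 12 months.

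**The concern.** The grouping rule for efficacy assumes that each child has one dose. The protocol's own move rule can create children with two. For them, dose received could mean the first dose, the last dose, or the dose current at each visit, and neither document chooses between these.

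The choice matters because the endpoint is cumulative. Month 12 height growth is change from baseline divided by expected change, so a child moved at Month 6 carries six months of growth from the higher dose into the Month 12 value. Under the last-dose or by-visit reading, that value is counted at the lower dose. Each dose is tested separately against the reference population, so a continuing dose could be called effective partly on growth it did not produce.

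Protocol 6.6.1 requires a new dose level to be filled with treatment-naive children. It sets no such limit for an existing lower dose that receives moved children.

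**Working it through.** **Inputs from the documents (Protocol 9.2):** 54 randomised for 15 evaluable per dose; one-sided family-wise error 0.05 over 3 doses; variability 0.15, scale not stated; target 50% above reference; stated power over 90%.

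**Reproducing the plan's figures.**
- Per-dose alpha: 0.05/3 = 0.0167, which rounds to the stated 0.017.
- Attrition: 1 − 15/18 = 16.7%, and 45/(1 − 1/6) = 54, as stated.
- Power: reading 0.15 as an SD on the growth-ratio scale, a one-sample one-sided t-test of the mean ratio against 1.0 with n = 15 has noncentrality (0.5/0.15) × √15 = 12.9. Power is about 1.00, consistent with over 90%.

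**Assumptions for the illustration.** SD 0.15 on the ratio scale; linear growth; move at Month 6; a continuing lower dose with true ratio 1.0 and 15 children of its own; moved children counted at the lower dose; one-sample t-test at one-sided 0.017. The t-test stands in for the SAP's repeated-measures model.

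**Step 1: expected Month 12 ratio of a moved child.** With half the year on each dose:
- Discontinued dose truly 1.5: 0.5 × 1.5 + 0.5 × 1.0 = 1.25.
- Discontinued dose truly 1.25: 0.5 × 1.25 + 0.5 × 1.0 = 1.125.

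**Step 2: mean of the lower-dose group with m moved children.** Mean = (15 × 1.0 + m × moved mean)/(15 + m). For example, with a moved mean of 1.25:
- m = 3: (15 + 3.75)/18 = 1.042.
- m = 15: (15 + 18.75)/30 = 1.125.

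**Step 3: chance of declaring the ineffective lower dose effective** (100,000 simulated trials per cell).

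| Moved children | Discontinued dose 1.5 | Discontinued dose 1.25 |
|---|---|---|
| 0 | 0.017 | 0.016 |
| 3 | 0.083 | 0.049 |
| 5 | 0.19 | 0.085 |
| 9 | 0.56 | 0.20 |
| 15 | 0.94 | 0.46 |

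A later move gives larger figures. At Month 9 with 5 moved, the two columns become 0.30 and 0.14.

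**Step 4: the same children grouped by randomised dose.** The continuing arm holds only its own children, so its error stays at about 0.017 however many are moved. N and planned power do not change. The mixed exposure now sits in the discontinued arm. With all 15 of its children moved at Month 6, that arm averages 1.25 instead of 1.5 (power about 1.00), or 1.125 instead of 1.25 (power about 0.80).

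**Does other text settle the assignment?** It does not.
- Protocol 9.1.1 wants the Month 12 effect regardless of adherence to study drug, which fits poorly with as-received grouping.
- SAP 6.1.1.1 names a hypothetical strategy and drops data after drug discontinuation or rescue. A moved child is still on recifercept.
- SAP Appendix 1 keeps all data regardless of intercurrent events, which conflicts with SAP 6.1.1.1.
- None of the three mentions a change of dose.

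**The case against.** A reader might infer that as-received grouping breaks the randomisation behind the primary test. The documents do not support that. Protocol 9.1 and SAP 5.1 test each dose against an external reference population, and randomisation does not protect such a test. The harm there is mixed exposure. Loss of randomised groups matters for the dose-finding aim and for the pairwise differences in least-squares means that SAP 6.1.1.1 presents, although Protocol 9.2 and 9.5 say doses will not be compared.

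A reader might also infer that the arms will be mixed. That is conditional. The protocol synopsis says no dose changes are prospectively planned, while allowing them. Protocol 6.6.1 says only that doses may be adjusted after the interim. SAP 7.1 describes the interim as input to internal decisions on future studies, which needs reconciling with 6.6.1. If no dose is discontinued, only dosing errors or ad hoc changes separate received from randomised dose.

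The illustrated bias also depends on counting moved children at the lower dose. If received means first received, the groups nearly match randomisation and the bias largely disappears. Moving all 15 children at exactly Month 6 is a limiting case, and the true ratios are assumed.

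Two partial safeguards exist. The PPAS groups by randomised dose, but it is a restricted sensitivity set. The protocol's change history for Amendment 1 refers to a primary analysis in treatment-naive participants, but the current 6.6.1 applies that requirement only to a new dose level.

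These points limit the size and likelihood of the harm. They do not supply the missing rule.

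**Conclusion.** The point holds as a gap in the analysis rules: the plan permits a child to receive two doses, groups efficacy by dose received, and does not say where that child is counted or how later heights are used. Under the least favourable reading, with the assumptions above, the false-positive rate for a continuing dose of no effect rises from 0.017 to between about 0.05 and 0.08 with 3 moved children, and to between 0.46 and 0.94 with 15. These figures show sensitivity to the missing rule; they do not forecast what the trial will find. The change should be made before results are seen, because the choice of reading could then affect which dose is called positive.

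**What to change.** In Protocol 9.3 and SAP 4, split the combined set. The efficacy FAS would be all randomised and dosed children, grouped by randomised dose. The Safety set would be all dosed children, grouped by dose received.

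Name a protocol-permitted change of dose as an intercurrent event. For the primary analysis, keep the child in the randomised arm and use all heights (treatment policy), which matches the wording of Protocol 9.1.1. Add a sensitivity analysis that excludes heights after the move. Align Protocol 9.1.1 with SAP 2.1.1, 6.1.1.1, 7.2 and Appendix 1, which currently differ on which data are kept. Reconcile Protocol 6.6.1 with SAP 7.1 on what the interim may lead to.

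The cost is two rows in each analysis-set table plus the estimand and intercurrent-event text, with a protocol amendment if this counts as a major change to the primary analysis. No extra children or data are needed, and planned power is unchanged. The downside is small: a discontinued arm's Month 12 estimate will reflect mixed exposure and must be labelled so.

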9.4. Statistical Analyses

The SAP will be developed and finalized before database lock and will describe the analyses and procedures for accounting for missing, unused, and spurious data. This section is a summary of the planned statistical analyses of the primary and secondary endpoints.

9.4.1. General Considerations

Data presented in tables will be summarized by reciferecept dose (defined in [Section 4.1](#)) and total. If needed summary presentations may also be grouped by gender. In addition, separate summaries will be completed for participants aged 3 months to <2 years (by dose, though not stratified by gender).

9.4.2. Primary Endpoint(s)

Efficacy

The primary efficacy endpoint of change from baseline of height at 12 months will be analyzed using an analysis of variance (ANOVA) model comprising terms for reciferecept dose groups. Change from baseline estimates for height and their corresponding 95% confidence intervals will be provided via least-square means. A Bonferroni adjustment will be applied to the 95% confidence intervals. The population for the primary analysis will be based on the FAS, while the PPAS is the population that will be used for sensitivity analysis.

Safety

The safety data will be summarized in accordance with Pfizer Data Standards. All participants who receive IP (safety population) will be included in the safety analyses. All safety data will be summarized descriptively through appropriate data tabulations, descriptive statistics, categorical summaries, and graphical presentations. Safety endpoints for the study include:

- TEAEs and SAEs;
- Withdrawals from treatment due to AEs.

Change from baseline in laboratory data and vital signs will be additionally summarized. Participant listings will also be produced for these safety endpoints.

PK Study Cohort:

The pharmacokinetic parameters following single dose administration in the PK cohort will be derived from the concentration-time profile as follows:

Parameter	Definition	Method of Determination
AUC _{inf}	Area under the serum concentration time profile from time 0 extrapolated to infinite time.	AUC _{last} + (C _{last} * / k _{el}), Where C _{last} * is the predicted serum concentration at the last quantifiable time point estimated from the loglinear regression analysis.
AUC ₁₆₈	Area under the serum concentration-time profile from 0 to 168 hours.	Linear/Log trapezoidal method.
AUC ₃₆₀	Area under the serum concentration-time profile from 0 to 360 hours.	Linear/Log trapezoidal method.
C _{max}	Maximum serum concentration.	Observed directly from data.
T _{max}	Time for C _{max} .	Observed directly from data as time of first occurrence.
t _{1/2}	Terminal elimination half-life.	Log _e (2)/k _{el} , where k _{el} is the terminal phase rate constant calculated by a linear regression of the loglinear concentration time curve. Only those data points judged to describe the terminal loglinear decline will be used in the regression.

Actual PK sampling times will be used in the derivation of PK parameters.

The serum PK parameters for recifercept will be summarized descriptively by formulation. Serum concentrations will be listed and summarized descriptively by formulation and nominal PK sampling time. Individual participant summary profiles (mean and median plots) of the serum-concentration time data will be plotted by formulation and PK sampling time. For summary statistics and summary plots, the nominal PK sampling time will be used. For individual participant plots, the actual PK sampling time will be used, whilst the pre-dose will be set to zero. Summary plots will be presented on both linear-linear and log-linear scales.

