3. OBJECTIVES, ESTIMANDS, AND ENDPOINTS

Objectives	Estimands	Endpoints
Primary:	Primary:	Primary:

• Evaluate the safety and tolerability of recifercept doses and dosing regimes in participants aged ≥ 2 to <11 years with achondroplasia.	N/A.	Safety and tolerability of recifercept as assessed through frequency and severity of AEs/SAEs.

• To assess efficacy of recifercept to increase height growth in children with achondroplasia.	
• The primary efficacy estimand is intended to provide a population level estimate of the effect of the IP on a continuous endpoint. Population-level summary: ratio between participants in the trial and a reference population [Merker et al, 2018]³⁰ in growth of height at 12 month; ratio between treated and reference population is observed change-from-baseline of treated participants standardized by reference participant given age and gender.	
• Increase in height growth above expected in reference population [Merker et al, 2018].³⁰
Secondary:	Secondary:	Secondary:

• To evaluate the pharmacokinetics (PK) of recifercept in children aged ≥ 2 to <11 years old with achondroplasia.		Population PK characterization in children aged ≥ 2 to <11 years old with achondroplasia. Clearance (CL/F) and other PK parameters of recifercept to assess exposures in different age group.

• To assess efficacy of recifercept to improve achondroplasia-related complications.		
• Sitting height/standing height ratio.• Arm span to height/length difference.

Objectives	Estimands	Endpoints
		
• Knee height:lower segment ratio.• Occipito-frontal circumference.• Ratio of occipito-frontal distance to occipito-mid-face measurements.• z-score of the above proportionality and skull morphology where achondroplasia reference datasets exist (occipito-frontal circumference, arm span, sitting height).• Fixed flexion angles at elbow.• Polysomnography parameters in those with pre-existing sleep-disordered breathing at the time of enrollment.• Body mass index (BMI).• Waist:chest circumference ratio.• Change from baseline in CHAQ (adapted for achondroplasia) component and index scores, QoLISSY Brief total score.

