9. STATISTICAL CONSIDERATIONS

Detailed methodology for summary and statistical analyses of the data collected in this study is outlined here and further detailed in a SAP, which will be maintained by the sponsor. The SAP may modify what is outlined in the protocol where appropriate; however, any major modifications of the primary endpoint definitions or their analyses will also be reflected in a protocol amendment.

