9.1. Estimands and Statistical Hypotheses

Height Growth Endpoint

Null hypothesis for height growth in this study is that height 12 months post-baseline for children on recifercept is equal to the expected height growth for the achondroplasia reference population based on Merker (2018).³⁰ The alternative hypothesis is that height growth for recifercept-treated participant is greater than the expected growth for achondroplasia reference population based on Merker (2018).³⁰

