9.1.1. Estimands

The primary efficacy estimand will be the population treatment effect of the mean change-from-baseline of a continuous response (ie, height growth) at month 12 irrespective of IP compliance. Increase in height growth above expected growth in reference population, a co-primary endpoint, is defined as the height growth in the achondroplasia reference population +50%. Intercurrent event for the efficacy estimand: withdrawal and all events leading missing data will be excluded from efficacy analysis and will not have their data imputed. The population-based treatment effect will be the mean change-from-baseline at 12 months.

The secondary estimand will be the population treatment effect of the mean change from baseline of a continuous response, defined as the decline in the difference of arm span to standing height. Intercurrent event for the efficacy estimand: withdrawal and all events leading missing data will be excluded from efficacy analysis and will not have their data imputed.

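### The protocol's dose-only ANOVA of height change omits the comparison with reference growth, and neither document keeps to one scale, one model and one test for the primary efficacy endpoint

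*Protocol*

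**What the plan says.** **Protocol.** Section 3 gives the efficacy summary as a ratio: "ratio between treated and reference population is observed change-from-baseline of treated participants standardized by reference participant given age and gender". Section 9.1 sets the null as growth on recifercept being "equal to the expected height growth for the achondroplasia reference population", with a one-sided alternative. Section 9.2 plans for growth 50% above reference with "inter-participant variability of .15 (estimated from C4181001", 15 evaluable children per dose and one-sided 0.017, and excludes comparisons between doses.

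Two places depart from this. Section 9.1.1 mentions reference growth plus 50% when it defines the endpoint, but states the treatment effect as the "population treatment effect of the mean change-from-baseline of a continuous response (ie, height growth) at month 12 irrespective of IP compliance". Section 9.4.2 specifies that "change from baseline of height at 12 months will be analyzed using an analysis of variance (ANOVA) model comprising terms for" the dose groups, reported as LS means with Bonferroni-adjusted 95% intervals. No reference, age, sex or comparison value appears there.

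**SAP.** Sections 2.1.1 and Appendix 2.2 define height growth as observed divided by expected change. Section 6.1.1.1 says that change relative to the reference "will be analyzed using MMRM including data from Months 3, 6, 9, and 12 with gender (and possibly age) as a covariate". The LS means it then presents are for change in standing height. Appendix 1 makes MMRM the main analysis and ANOVA the per-protocol sensitivity analysis.

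**Amendment rule.** Protocol section 9 lets the SAP modify the plan, but "any major modifications of the primary endpoint definitions or their analyses will also be reflected in a protocol amendment". SAP section 2 repeats this.

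**The concern.** The trial has no concurrent control. Efficacy rests entirely on comparing each dose with growth expected for age and sex, so that comparison must be in the primary analysis. In protocol 9.4.2 it is absent. The overall test of a dose-only ANOVA compares the doses with each other, which 9.2 excludes. The usual test of an LS mean is against zero, which growing untreated children also exceed. If a reader supplies one reference value in cm, the answer depends on the age mix of each arm, and enrolment is staggered by age and dose (protocol 4.1).

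The SAP does not settle the matter, because it moves between the ratio and standing height. At database lock the analyst would have to choose the scale, the model and the comparison value. For an externally referenced claim, those choices should be closed in advance.

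**Working it through.** **1. The plan's power figure.** Inputs from protocol 9.2: ratio 1.5 against 1, SD 0.15 (no unit given; taken here as the SD of the ratio), n = 15, one-sided 0.017. The noncentrality is 0.5 / (0.15/√15) = 12.9, so one-sample t power exceeds 99.9%. The stated figure of over 90% is reproduced as a lower bound. It relies on a relative scale: a 50% effect and an SD of 0.15 fit together only as parts of a ratio.

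**2. Scale, place by place.**

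| Place | Scale |
|---|---|
| Protocol 3, 9.1, 9.2 | Relative to reference |
| Protocol 9.1.1 (treatment effect), 9.4.2 | Change in height |
| SAP 2.1.1, Appendix 2.2 | Ratio |
| SAP 6.1.1.1, method | Change relative to reference |
| SAP 6.1.1.1, LS means presented | Change in standing height |
| SAP Appendix 1 | Change in standing height |
| SAP Appendix 4, code | Response is height |

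**3. Model.** SAP 5.2.1 includes treatment-by-visit, age and gender. Section 6.1.1.1 makes age optional. Appendix 1 includes age. The Appendix 4 code includes age but has no dose-by-month term, so its dose LS mean is an average over visits. The code requests no Month 12 estimate and no test against 1.

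**4. Intervals.** If two-sided, a Bonferroni-adjusted 95% interval has level 1 - 0.05/3 = 98.33%, or 0.0083 per tail. The decision rule has 0.05/3 = 0.0167 in one tail, which corresponds to a 96.67% two-sided interval. The SAP's unadjusted 95% interval has 0.025 per tail. Neither matches the rule.

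**5. What the literal analysis does when the drug has no effect (illustration).** Assumptions not in the documents: expected growth falls linearly between ages 2 and 11 at the rates below, and ages are uniform. Other settings: ratio SD 0.15, 15 per arm, one-sided 0.017, 20,000 simulated trials per row. The fixed cm reference is the mean of the two end rates. The default LS-mean test against zero rejected in 100% of trials. Per-dose rejection rates otherwise were:

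| Growth at age 2 → 11 (cm/year) | Fixed cm reference, all arms aged 2-11 | Fixed cm reference, arm aged 2-8 | Ratio against 1, arm aged 2-8 |
|---|---|---|---|
| 5 → 4 | 0.015-0.017 | 0.10 | 0.017 |
| 6 → 4 | 0.016-0.017 | 0.21 | 0.018 |
| 6 → 3 | 0.016-0.017 | 0.35 | 0.018 |
| 8 → 3 | 0.017-0.018 | 0.43 | 0.017 |

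**6. A milder illustration.** Assume mean expected growth of 5 cm/year.

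- *Spread.* If expected growth is uniform over 4-6 cm, its CV is (2/√12)/5 = 0.115. The relative SD becomes √(0.15² + 0.115²) = 0.19, and intervals are 1.26 times as wide. Over 3.5-6.5 cm the CV is 0.173, the SD 0.23 and the factor 1.53.
- *Shift.* If under-6s are expected to grow 5.5 cm and older children 4.5 cm, a 20-point difference in age mix moves a dose mean by 0.20 × 1 cm = 0.2 cm, or 4%.
- *Threshold.* The smallest significant gain is t × SD/√15, with t = 2.20 (42 df) to 2.36 (14 df). That is 11-12% at SD 0.19 and 13-14% at SD 0.23, so the shift is 29-37% of it.
- *Error.* With the 4% shift, per-dose error is 0.085-0.092 at SD 0.19 and 0.066-0.071 at SD 0.23.
- *Power.* For +50% at SD 0.23, n = 15 and one-sided 0.05/3, power is still above 99.9%.

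**The case against.** The best defence is that 9.4.2 should be read with section 3. It states no unit, and section 9.4 calls itself a summary, with detail left to the SAP. A dose-only ANOVA on the section 3 ratio, with each LS mean read against 1, would test the 9.1 null, because age, sex and the reference are already in the denominator. This stands as a possible reading. A reader might infer that the protocol's model cannot test its null at all, or that it is expressly in cm; the text does not go that far. But 9.4.2 says neither ratio nor 1, and the literal wording of 9.1.1 and 9.4.2 points to height change.

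A reader might also infer that the SAP introduced a new scale without an amendment. It did not: the ratio is in protocol section 3 and underlies 9.2. Only the move from ANOVA to MMRM clearly engages the amendment promise. The SAP may modify the protocol, and whether this change is major is a judgement. Against treating it as minor, the protocol's document history lists the clarification of ANOVA rather than ANCOVA in 9.4.2 under Amendment 1, among changes classed as substantial. An amendment outside the supplied text cannot be excluded, and SAP version 1 is not available.

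The absence of covariates from the protocol's ANOVA looks deliberate, since the same history records removal of stratification. On the ratio scale, further adjustment for age and sex is largely a matter of preference. Leaving age optional is therefore a small point, though it should still be closed.

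**Conclusion.** The point holds in three parts.

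1. Protocol 9.4.2, and the treatment effect stated in 9.1.1, lack the comparison with expected growth that sections 3, 9.1 and 9.2 require.
2. The scale conflict lies inside each document, not between a protocol in cm and a SAP in ratios. Adopting the SAP's analysis as it stands would therefore not resolve it.
3. MMRM replaces ANOVA in the SAP with no matching text in the supplied protocol.

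The numerical consequence is illustrative only. Growth rates and age imbalance are assumptions. The protocol makes imbalance plausible: enrolment is staggered, and 14, 15 and 3 children were on the low, medium and high dose by September 2021 (2.2.1). It does not give the final age mix. Under the assumptions shown, a fixed cm reference with one younger arm gives per-dose error of 0.10-0.43, and the milder case gives 0.066-0.092, against 0.017 planned. A reader might infer that the trial is underpowered on this account. It is not: power for +50% stays above 99.9% even at SD 0.23. What is at stake is the validity and pre-specification of the claim against the reference, so this should be corrected before the primary analysis.

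**What to change.** Make protocol 9.1.1 and 9.4.2 and SAP 6.1.1.1, Appendix 1 and the Appendix 4 code state the same three things:

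- **Endpoint:** H = observed/expected growth at Month 12, as in SAP Appendix 2.2.
- **Model:** MMRM on H with dose, visit, dose-by-visit, sex and age, deleting the word possibly from SAP 6.1.1.1.
- **Test:** each dose's Month 12 LS mean against 1 at one-sided 0.05/3, with intervals at the matching level (96.67% two-sided, or a one-sided 98.33% lower bound).

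In the code, the response becomes H, a dose-by-month term is added, and the Month 12 LS means are requested with 1 as the null value. Keep change in height in cm as a descriptive table.

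The cost is one protocol amendment and several SAP edits. No visit, measurement or sample-size change is needed.
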